## Implementation of HIV Pre-Exposure Prophylaxis (PrEP) among People Who Inject Drugs (PWID) in Ukraine

### SCHEMA

Purpose:	To assess the acceptability and feasibility of PrEP for People Who Inject Drugs (PWID) in Kyiv, Ukraine with and without SMS facilitation.
Design:	An 24-week prospective randomized controlled trial of PrEP as usual versus PrEP with SMS facilitation
Population:	HIV-uninfected PWID at risk for HIV infection in Kyiv, Ukraine.
Study Size:	A total of 200 participants randomized 1:1 to experimental and control arms.
Study Regimen:	All participants will be offered once daily oral emtricitabine 200 mg / tenofovir disoproxil fumarate 300 mg (FTC/TDF) combined with SMS facilitation in the experimental arm.
Study Duration:	12 months including closeout activities. Preparatory phase is planned to take 2 months. Recruitment is anticipated to take place over a 2-month period. Each participant will be followed for a total of 6 months. Two months are included for data clean-up and closeout.
Primary Objectives:	To compare adherence to and persistence on daily PrEP prescribed as the fixed dose formulation to PWID randomized 1:1 to PrEP as usual or SMS-enhanced PrEP.
Secondary Objectives:	

 To describe patterns and attributes of PrEP adherence among participants (e.g., SMS intervention acceptance, substance use, sociocultural factors)

 To measure changes in injection and sexual risk taking behavior among study participants

 To describe client- and provider-level barriers to PrEP initiation and adherence

Study Sites:	

 Institute of Epidemiology and Infectious Diseases (Lavra) Clinic

 Club Eney Community Center

---

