### 3.0 STUDY POPULATION

The study will enroll 200 eligible HIV-uninfected PWID, 100 at each site. Participants will be selected for the study according to the criteria specified below. They will be recruited, screened and enrolled as described in Section 3.3. Issues related to participant retention and withdrawals from the study are described in Sections 3.4 and 3.5, respectively.

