#### 3.2 Exclusion Criteria

PWID who meet any of the following criteria will be excluded from this study:

- Any reactive or positive HIV test at Screening
- Any reactive or positive HBsAg test at Screening
- Serum creatinine < upper limit of normal (ULN) and calculated creatinine clearance of at least 60 mL/min by the Cockcroft-Gault formula where:
  - $eCcr \text{ in mL/min} = [(140 - \text{age in years}) \times (\text{actual body weight in kg})] / (72 \times \text{serum creatinine in mg/dL})$
- Planning to move out of the area or to travel for more than 3 months during the study follow-up period
- Unwilling to adhere to study procedures
- Use of ARV drugs (PrEP or PEP) in the last 60 days prior to anticipated enrollment by self-report
- Prior history of a gastrectomy, colostomy, ileostomy, or any other procedure altering the gastrointestinal tract or drug absorption (provided by self-report, or obtained from medical history or records)
- Any condition, that in the opinion of study staff, would make participation in the study unsafe, or interfere with achieving the study objective

Any person who cannot provide informed consent will be excluded from participation in the project. Staff conducting screening will be trained to identify participants who cannot provide appropriate informed consent. If it is determined that the inability to provide informed consent is due to a temporary/situational factor (e.g., intoxication), these persons will be given the opportunity to reschedule their enrollment appointment as appropriate. All participants will be afforded the same protections.

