### **5.2 Enrollment Visit**

The enrollment visit will take place at a clinical facility designated as a PrEP provider for the study. All procedures will be conducted by the research/intervention staff in close collaboration with the clinical staff. A participant is considered enrolled at the point in time when all enrollment visit procedures are complete.

The following procedures are included in the Enrollment visit (actual sequence may differ).

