#### **2. Informed consent**

Prior to screening, every potential participant demonstrating interest in study participation will have to sign the Informed Consent Form (See Appendix III). Consent procedure will be performed by a study staff member responsible for recruitment. In more details, the consent procedure is described in Section 8.

3. Randomization

Consenting participants will be randomized using the functionality in REDCap participant database using a pre-defined allocation schedule stratified by site.

4. Locator information

After signing the ICF, the participant will provide his contact information. Staff members will assure participants that the detailed follow-up information will be deleted if they are not enrolled in the study.

5. Behavioral and psychosocial survey

Structured interviews will be administered by an experienced interviewer using the questionnaire designed by study team (Appendix II). Baseline and follow-up questionnaires will not differ in content. Interview data will be directly entered into the online version of the participant questionnaire at the REDCap platform.

*Intervention provision (intervention staff)*

6. Assess participant's readiness for PrEP adherence

PNs will use a PrEP readiness tool to assess key predictors of PrEP adherence.

7. PrEP discussion

PrEP Education will be provided at each study visit to participants by PrEP Navigators with the option to start/continue, stop, or abstain from usage. A manual will be created for all sites to follow when discussing PrEP with participants based on safety and efficacy language found in the ICF under "Study Purpose".

8. Autonomy supportive adherence counseling

Adherence counseling will be provided to all participants who initiate PrEP at each study visit starting at the enrollment visit. The counseling makes use of self-determination theory that is designed to facilitate the client's integration of PrEP usage into his health behavioral routines and support the client in making his own decisions regarding adherence. Counseling will include the development of client-centered strategies to support the consistent daily adherence of PrEP. This counseling is delivered one-on-one by PrEP navigators during the study visits. The counseling will also include reminders not to share the medication and to contact project staff with questions about product use.

After each counseling session, the PN will fill out the Care Coordination Measurement Tool (CCMT).

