HIV testing will be conducted according to the current HIV testing guidelines by trained staff, with pre- and post-test counseling. According to Ukrainian legislature, HIV diagnosis cannot be made at any setting other than an accredited governmental HIV lab. Therefore, a positive result of rapid testing (regardless of the number of confirmatory runs) will be explained to a subject as preliminary and insufficient to definitively confirm HIV infection, which can be done at specialized health care institutions. As specified in the National HTC guidelines, post-test counseling will provide all details on where the confirmatory testing can be done, and appropriate referrals will be provided.

Participants who test HIV positive will be withdrawn from the study at this point.

16. HBsAg testing

Testing for Hepatitis B is needed because the drugs used in Tenof-EM® can also be used to treat hepatitis B virus and taking Tenof-EM® now might result in less effective treatments for hepatitis B. Testing will be done using a venous blood sample with test kits available at the clinic. Participants positive for HBsAg will be excluded from the study and will be provided appropriate counseling.

17. Blood collection for creatinine test with subsequent calculation of creatinine clearance

To verify eligibility, participants will provide a venous blood sample for the creatinine test. Routinely, the test results will be available within 3 days. Considering the low expected prevalence of elevated creatinine levels, PrEP will be dispensed at the same visit before the creatinine test result is available. If an elevated level is detected, the participant will be contacted, instructed to discontinue PrEP medication and invited for an interim visit to the clinician for a thorough assessment of renal function and possible reasons for elevated creatinine.

18. DBS storage for pharmacology testing

DBS samples will be processed and stored for all participants; testing may be limited to a subset of these samples. DBS will be stored at -20° C within 24 hours of collection and shipped in bulk to a centralized laboratory on dry ice for testing. TDF will be quantified with a validated liquid chromatography tandem mass spectrometry method.

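### The protocol lets consenting participants be randomised, in an open-label trial, before the baseline survey and most eligibility checks, and as listed it describes that order

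*Protocol*

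**What the plan says.** Section 5.2, item 3, fixes who is randomised: "Consenting participants will be randomized using the functionality in REDCap participant database using a pre-defined allocation schedule stratified by site". The condition is consent, not confirmed eligibility. The numbered list then runs: locator data (4), baseline survey (5), readiness assessment (6), PrEP discussion, counselling and supply (7 to 9), SMS customization and test for the experimental arm (10 and 11), risk-reduction counselling (12), medical history (13), physical examination (14), HIV test (15), HBsAg (16) and creatinine (17).

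The consequences of failing attach at the later items. For HIV: "Participants who test HIV positive will be withdrawn from the study at this point". For HBsAg: "Participants positive for HBsAg will be excluded from the study". The creatinine result, needed to verify eligibility, is routinely available within 3 days.

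Enrolment is defined separately from randomisation: "A participant is considered enrolled at the point in time when all enrollment visit procedures are complete". The order is not binding: "The following procedures are included in the Enrollment visit (actual sequence may differ". Sections 3.2, 5.9 and 9.1 place the HIV test at Screening (3.2 also the HBsAg test), but Appendix I has no Screening visit. It puts consent and randomisation in one row under Enrollment, with the survey and all laboratory tests in the same column.

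Section 3.2 includes a discretionary exclusion: "Any condition, that in the opinion of study staff, would make participation in the study unsafe, or interfere with achieving the study objective". Section 7.1 calls the trial open-label.

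The target is stated in two ways. The Schema has "A total of 200 participants randomized 1:1 to experimental and control arms"; section 3.0 has "The study will enroll 200 eligible HIV-uninfected PWID, 100 at each site".

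**The concern.** Once the arm is known, any later decision that rests on judgement can be affected by it. Four steps are exposed here: the staff-opinion exclusion, the clinician's review of history and contraindications, the participant's own decision to stay, and the answers given to the interviewer at baseline. The survey (Appendix II) covers use of reminders, perceived competence for PrEP use, and injection and sexual risk behaviour, and it is the baseline for the risk-behaviour endpoint.

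Selective loss is also hard to see afterwards. A person can be randomised but never enrolled, and section 5.7 deletes the data of anyone who chooses to withdraw. A participant who learns the arm and leaves could therefore drop out of the comparison altogether.

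Laboratory exclusions are a different matter. Knowing the arm hardly changes a test result, so these mainly cost numbers and leave it unclear who is counted.

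**Working it through.** **Is allocation conditional on anything but consent?** Item 3 names only consent. Neither section 5.2, section 3 nor Appendix I states that eligibility or the survey must be complete first. So the protocol permits early allocation.

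**Is early allocation certain?** Each step in turn:

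| Step | Listed position | Evidence on timing | Conclusion |
|---|---|---|---|
| Baseline survey | item 5 | sequence may differ | may follow allocation |
| Medical history | item 13 | sequence may differ | may follow allocation |
| HIV test | item 15 | sections 3.2, 5.9 and 9.1 say Screening; Appendix I says Enrollment | ambiguous |
| HBsAg test | item 16 | section 3.2 says Screening; Appendix I says Enrollment | ambiguous |
| Creatinine result | item 17 | routinely within 3 days of the visit | follows allocation made at that visit |

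**When is the arm revealed?** At the latest at items 10 and 11, because only the experimental arm sets up SMS. As listed, that is ahead of items 13 to 17.

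**What happens to the numbers?** The plan gives no figure for failures after randomisation. Section 7.2 allows for 10% to 20% loss to follow-up only. Let q be the assumed share of those randomised who prove ineligible.

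- Eligible out of 200 randomised = 200 × (1 − q).
- Randomised to obtain 200 eligible = 200 / (1 − q), rounded up.
- Power for an assumed contrast of 33% v 50%, two-sided 5%, with n = 100 × (1 − q) per arm, if those who fail are left out. The formula is Φ([0.17 − 1.96 × √(2 × 0.415 × 0.585 / n)] / √((0.33 × 0.67 + 0.50 × 0.50) / n)). The protocol states no such contrast; it is used for scale only.

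| q (assumed) | Eligible of 200 | Randomise for 200 eligible | Power |
|---|---|---|---|
| 0% | 200 | 200 | 68.7% |
| 2% | 196 | 205 | 67.8% |
| 5% | 190 | 211 | 66.4% |
| 10% | 180 | 223 | 64.1% |
| 15% | 170 | 236 | 61.6% |
| 20% | 160 | 250 | 58.9% |

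**Chance imbalance.** If recruitment continues to about 200 eligible, the arm counts are two independent Binomial(N/2, 1 − q) variables. With q = 10%, 20% or 30% and N = 222, 250 or 286, the chance that they differ by 10 or more is 0.033, 0.133 or 0.220. This is chance imbalance, not bias.

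**The case against.** The strongest reply is that a list is being read as a timetable. Section 5.2 disclaims the order and groups the items by staff role. The numbering cannot be literal: eligibility screening is item 1 and consent item 2, yet the text requires consent before screening. Item 17 mentions only creatinine as pending when drug is dispensed, which suggests that the HIV and HBsAg results are already in hand. This stands. A reader might infer that participants are always randomised before HIV and HBsAg status is known; the documents do not establish that. They also do not prevent it, and an order left to staff can vary by site or by participant.

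A reader might also infer that 200 randomised and 200 eligible and enrolled cannot both hold, or that the number analysable must fall below 200. Neither follows. Both hold if screening comes first or nobody fails afterwards, and section 3.3 recruits until the target is reached.

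Nor do staff-excluded participants disappear. Section 5.7 deletes data only when a participant chooses to withdraw and uses the information in all other cases; item 4 deletes only the follow-up contact details of those not enrolled.

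The bias is bounded too. Both arms are offered the same drug, so contraindications do not depend on arm. The binary primary outcome is drug concentration in dried blood spots, not self-report. Risk behaviour is a secondary endpoint with mostly descriptive analysis. An arm difference of 10 costs almost nothing: 105 v 95 has an effective size of 4 × 105 × 95 / 200 = 199.5. All of this stands, and it limits the point to judgement-based exclusions, departures after allocation, and baseline interviews.

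Finally, analysis sets are often left to the SAP, which is not at hand. That is fair for the handling of later-ineligible participants, but not for the timing of allocation or the meaning of 200, which the protocol itself sets.

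**Conclusion.** The point holds as a gap in the allocation procedure. The protocol conditions randomisation on consent alone, and its listed order puts the arm in the open before the clinical and laboratory checks. The baseline survey is listed after allocation. Delay past allocation is certain only for creatinine, on the Appendix I reading that randomisation takes place at the Enrollment visit. A high creatinine leads to stopping PrEP and an interim visit; whether that person remains in the study population is not stated.

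The size of any bias cannot be computed from the documents. The loss of numbers depends on an assumed failure rate: between 2% and 20%, 200 randomised leaves 196 to 160 eligible, and illustrative power for 33% v 50% falls from 68.7% to between 67.8% and 58.9% if failures are not replaced. The stronger claims, that early allocation always happens and that the two statements of 200 are irreconcilable, are not supported. The change is still worth making before the first participant is randomised, because the order of allocation cannot be repaired afterwards.

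**What to change.** 1. Reword item 3 so that participants are randomised only after consent, the baseline survey, the readiness assessment, the medical history and the available HIV and HBsAg results have confirmed eligibility, and immediately before SMS customization. Moving item 3 to just before item 10 is not enough by itself: the medical and rapid-test items (13, 15 and 16) must move ahead of it. State this as a condition and exempt it from the note that the sequence may differ.
2. State that anyone found ineligible after randomisation, including on the delayed creatinine result, remains in the randomised analysis set in the allocated arm.
3. State once whether 200 counts participants randomised (Schema) or eligible and enrolled (section 3.0).
4. Reconcile the Screening visit named in sections 5.9 and 9.1 with Appendix I, which has none.

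The cost is reordering the REDCap form and the SOP, plus some baseline surveys spent on participants who then fail screening. No extra tests are needed.

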### 5.3 Month 1, 3 and Month 6 (exit visit)

At months 1 and 3, the participants will visit the clinical site to complete the assessments and receive the medication supply for next two (at month 1) three (at month 3) months. At month 6, participants will not receive medication as a part of the study, but will be referred to other available PrEP providers in Kyiv. The following procedures will be included.

- Verify locator information
- Behavioral and psychosocial survey
- Self-reported study product adherence assessment
- PrEP discussion
- PrEP Navigation and study product supply
- Autonomy supportive adherence counseling
- SMS reminder customization

- HIV/ STI behavioral risk-reduction counseling, provision of prevention supplies
- Medical history including but not limited to co-morbidities, concomitant medications, HIV risk history
- Symptom-driven physical exam
- AE Assessment
- HIV rapid test – at months 3 and 6.
- DBS storage for pharmacology testing
- Urine storage for substance use testing

The exit visit will include all procedures for Month 3, except for PrEP provision and related counseling and SMS customization.

#### 5.4 Months 2, 4, 5

Monthly assessments between the PrEP dispensing visits (Enrollment and 3-month) will be conducted by research staff **by telephone**. The following procedures will be included.

- Review and update locator information
- Self-reported study product adherence assessment

Self-reported PrEP adherence for all participants will be assessed using both a visual analogue scale (VAS) and a new 3-item self-report measure. The VAS is empirically validated, consistently under-reports adherence, but effectively measures a “difference” in adherence that changes in response to an intervention. The 3-item adherence self-report scale showed good psychometric characteristics and good construct validity when compared with an drug monitoring standard. Two self-report adherence measures are often recommended.

- PrEP discussion
- Autonomy supportive adherence counseling
- SMS reminder customization

Experimental arm participants will have an opportunity to change the parameters of the SMS reminders.

- HIV/ STI behavioral risk-reduction counseling

After the standard risk-reduction counseling, the participants will be invited to visit the harm reduction site to receive supplies.

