#### 5.5 Interim Visits

Interim visits may occur at any time during the project and may be conducted at the clinic or at the affiliated community sites. Interim visits may occur for one or more of the following reasons: 1) Medical reasons (e.g., a client may want to discuss barriers to adherence not related to side effects; client may require an interim visit related to a priority health issues; client may require STD/HIV screening); 2) Reasons related to an adverse event for example, intolerable side effects; 3) Other reasons the participant may request. In general, participants requesting interim visits should contact their PN for triage. The PN will make a recommendation to the client on whether an interim visit is indicated or whether an alternate plan is warranted.

When interim visits in response to participant reports of AEs are completed, the physician, physician’s assistant or nurse practitioner member of the clinical team will clinically assess the reported event and provide appropriate medical care or make appropriate referrals. Participants with symptoms suggestive of acute HIV-infection syndrome will receive diagnostic testing to attempt to elucidate the cause of the syndrome, including HIV testing that includes testing for HIV RNA. Study medication will be stopped immediately if any HIV test is reactive or positive. All interim visits will be documented in the client’s clinical/study records. All interim clinical visits identified in the health information exchange from client’s primary or other health care provider (when applicable) will also be noted in the client’s clinical/study records and on applicable CRFs.

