## 6.2 Adverse Event (AE) Reporting

Adverse events (AE) are defined as any untoward medical occurrence experienced by participants during the study, and may or may not have a causal relationship with the treatment. Information regarding all AEs regardless of seriousness or severity will be recorded in the participant's source files. Grade 3 and higher adverse events and all creatinine AEs will be recorded on study CRFs. All SAEs must be reported on AE Log CRF. All AEs that result in a clinical hold or permanent discontinuation of study product are reported on AE Log CRF regardless of grade. Grade 3 and higher clinical AEs will be referred to a study clinician at the time of the visit.

All critical laboratory values will be reported as applicable per site SOPs. Participants who are not present at the study site at the time a laboratory AE requiring retesting or follow-up is identified will be followed as deemed clinically appropriate. With appropriate permission of the participant, and whenever possible, records from non-study medical providers related to untoward medical occurrences will be requested and required data elements will be recorded on study CRFs and/or in the participant's medical chart. All AEs regardless of severity will be followed clinically, until the AE resolves or stabilizes as per the appropriate toxicity algorithm. AEs will be assessed for all participants, regardless if they continue PrEP or not, after enrollment through the final study visit.

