### 7.3.2 Secondary Analyses

Analyses for secondary objectives will be mostly descriptive. Line listings as well as summary descriptive statistics including means, medians, and proportions with 95% exact or asymptotic confidence intervals as appropriate at each visit, will be used for the following secondary objectives. Specifically,

- Use GEE or random effects models to describe longitudinal patterns and their correlates of PrEP adherence among participants (e.g.: substance use, sociodemographics, sociocultural factors, risk practices and incarceration)
- To describe side effects and adverse events of PrEP among participants in the PrEP demonstration project. AEs will be tabulated, overall and by grade. For any reasonably common AEs (> 20 events), exploratory analyses will be conducted to assess correlates of the AE, including demographics and duration and patterns of PrEP use, within the limits imposed by the small expected number of events.
- Describe and produce summary plots for longitudinal changes in sexual risk-taking behavior among study participants
- List and summarize reasons PWID choose to initiate or decline PrEP
- List and summarize HIV seroconversions and characteristics of the infection(s) (e.g., viral set point, drug resistance patterns) in participants who initiated PrEP

- Use Kappa-statistics to assess agreement of adherence under different measures.

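### Scheduled adverse-event questioning looks back over 1, 2 and then 3 months, so any analysis of AEs by duration of PrEP use is partly confounded with ascertainment

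*Protocol*

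**What the plan says.** - **Clinic visits (5.3).** The procedures for Months 1, 3 and 6 include "AE Assessment". Month 6 keeps it: "The exit visit will include all procedures for Month 3, except for PrEP provision and related counseling and SMS customization".
- **Telephone contacts (5.4).** "Monthly assessments between the PrEP dispensing visits (Enrollment and 3-month) will be conducted by research staff". The listed content is locator review, self-reported adherence, PrEP discussion, adherence counseling, SMS customization and risk-reduction counseling. AE assessment is not listed.
- **Supply (5.3).** Medication dispensed at Month 3 covers the following three months.
- **Appendix I.** There is no AE assessment row for any visit. Medical history and symptom-driven examination are marked at Enrollment only, although 5.3 lists both at Months 1, 3 and 6. Creatinine is marked at Enrollment only.
- **Other routes of capture.** Section 5.5 allows interim visits at any time, including for "2) Reasons related to an adverse event for example, intolerable side effects". Sections 5.5 and 6.2 also provide for information from outside providers.
- **Coverage promised (6.2).** "AEs will be assessed for all participants, regardless if they continue PrEP or not, after enrollment through the final study visit".
- **What reaches the CRF (6.2).** "Grade 3 and higher adverse events and all creatinine AEs will be recorded on study CRFs", together with SAEs and AEs that lead to a hold or discontinuation. All AEs go into the source files.
- **Analysis (7.3.2).** The plan is that "exploratory analyses will be conducted to assess correlates of the AE, including demographics and duration and patterns of PrEP use". This step applies only above a frequency threshold, which the section words as "For any reasonably common AEs (> 20 events".

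**The concern.** The time between scheduled AE questions lengthens as follow-up proceeds. Most participants receive their first supply at enrollment, so time on PrEP and length of the look-back period grow together. An analysis of AEs by duration of use then cannot cleanly separate a real change in tolerability from a change in how events were ascertained. If recall fades, side effects could appear to wane more than they do.

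There is also a monitoring aspect. Under 6.1 the monitoring committee reviews safety about monthly. Between Months 3 and 6, which is half of follow-up and runs on one supply, a participant is asked no scheduled AE question until the exit visit. Yet staff telephone twice in that time. Apart from the restart procedure in 5.6, no creatinine test is scheduled after Enrollment, so detection in this period rests largely on what participants report.

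**Working it through.** **1. Windows.** Scheduled AE questions fall at Months 1, 3 and 6 after enrollment at Month 0. The look-back lengths are 1 - 0 = 1, 3 - 1 = 2 and 6 - 3 = 3 months. The share of follow-up covered by a one-month window is 1/6, and by a three-month window 3/6.

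**2. No figure to reproduce.** The protocol states no AE rate, no recall period and no recall loss. What follows is an illustration on assumptions.

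**3. Model (assumed).** The true AE rate is constant. An event that occurred t months before the question is reported with probability exp(-kt), where k = ln2/h and h is the recall half-life in months. The fraction captured over a window of L months is

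f(L) = (1 - exp(-kL)) / (kL), with f(L) = 1 when k = 0.

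Example, h = 1 (k = 0.693): f(1) = (1 - 0.5)/0.693 = 0.721 and f(3) = (1 - 0.125)/2.079 = 0.421. The ratio is 0.421/0.721 = 0.58.

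| h (months) | k | f(1), to Month 1 | f(2), Months 1-3 | f(3), Months 3-6 | f(3)/f(1) |
|---|---|---|---|---|---|
| no loss | 0 | 1.000 | 1.000 | 1.000 | 1.00 |
| 6 | 0.116 | 0.944 | 0.893 | 0.845 | 0.89 |
| 3 | 0.231 | 0.893 | 0.801 | 0.721 | 0.81 |
| 2 | 0.347 | 0.845 | 0.721 | 0.622 | 0.74 |
| 1 | 0.693 | 0.721 | 0.541 | 0.421 | 0.58 |

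**4. Allowing for interim visits (assumed share s of events caught without loss).** The captured fraction becomes s + (1 - s)f(L). With s = 0.5:
- h = 1: (0.5 + 0.5 × 0.4208)/(0.5 + 0.5 × 0.7213) = 0.7104/0.8607 = 0.825.
- h = 6: (0.5 + 0.5 × 0.845)/(0.5 + 0.5 × 0.944) = 0.923/0.972 = 0.95.

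**5. Counts instead of rates.** Events per visit, in units of the true monthly rate, are L × f(L). With no loss they are 1, 2 and 3. With h = 1 they are 0.72, 1.08 and 1.26. Uncorrected per-visit counts therefore rise, while rates per month stay flat or fall.

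**6. With monthly questioning.** Every window has L = 1, so the late-to-early ratio is f(1)/f(1) = 1.00 whatever the value of k.

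**The case against.** A reader might infer that the analysis must show a falling AE rate by construction. The documents do not support that. Unequal windows alone leave a rate unchanged (ratio 1.00 without recall loss), and per-visit counts would move the other way. A fall needs recall loss, which the protocol does not quantify, and an analysis in rates per interval, which it does not specify.

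A reader might also infer that events in Months 3-6 come to light only if the participant volunteers them. That is wrong too. The exit visit asks about that window, interim visits may occur at any time, and outside records are sought. Appendix II adds a side-effects form at follow-up and, in the adherence form, a block for those who discontinue.

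Further points on the other side:
- The analysis is exploratory, needs more than 20 events of one kind, and may mean comparing participants with different use histories. PrEP can be stopped and restarted, so duration of use is not the same as time since enrollment.
- CRF entries are mainly severe events, laboratory creatinine findings, SAEs and events that lead to a hold or discontinuation. These are plausibly less easily forgotten (a judgement).
- The treatment of exposure time is commonly left to an analysis plan, so its absence from 7.3.2 is not an error.

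These points limit the size and reach of the problem. They do not remove it. Interim visits depend on the participant making contact and on triage by the PrEP navigator, so they favour troublesome events. An AE frequent enough to pass 20 events among 200 participants is, in my judgement, more likely to be mild and forgettable. Onset dates or exposure time in an analysis cannot restore events that were never reported.

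**Conclusion.** The point holds as a modest design weakness. Scheduled AE questioning has windows of 1, 2 and 3 months, and these lengthen along largely the same axis as one of the named correlates. Any analysis of AEs by duration of use is thus partly confounded with ascertainment and may understate later rates if recall is lost.

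The size is unknown. On the assumed constant rate and exponential loss, the ratio of Months 3-6 to Month 1 lies between 1.00 and about 0.58. If half of all events are caught at interim visits, the one-month half-life gives about 0.83 instead of 0.58. The lower end is a pessimistic assumption, not an estimate.

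Both arms follow the same schedule, so the planned intervals create no difference between arms, and the adherence and persistence endpoints are untouched. The case for change rests on the low cost, on more even AE data and on earlier notice of events during the three-month supply. Separately, Appendix I and section 5.3 disagree on follow-up AE assessment, medical history and symptom-driven examination, and must be reconciled.

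**What to change.** 1. In section 5.4, add an AE assessment covering the time since last contact to the Month 2, 4 and 5 telephone procedures.
2. In Appendix I, add an AE assessment row marked for Months 1, 3 and 6, the telephone contacts and interim visits, so that the table agrees with 5.3. Reconcile the medical history and symptom-driven examination rows with 5.3 at the same time.
3. If the calls are left as they are, restrict any analysis by duration of use to comparisons with equal reporting windows, and say so when reporting it.

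**Cost.** No new visits or staff are needed. At most 200 × 3 = 600 existing calls become slightly longer, with some extra AE form entry. Handling of a reported event stays with the provisions already in sections 5.5 and 6.
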